8.2 Assess adherence

Primary Outcome 2: proportion of days for which EVOO was taken

Primary Outcome 3: proportion of days for which tree nuts were taken

Primary Outcome 4: proportion of days for which EVOO and tree nuts were taken

For adherence, we will examine the daily diaries for intake of the two study foods, tree nuts and EVOO. Adherence for each participant will be measured as the proportion of days in 4 weeks for which nuts, and of EVOO were taken, and by the proportion of days for which both were taken. Problems associated with consuming the study foods will be defined as non-adherence (ceasing to consume either or both study foods) and low adherence (not consuming both foods

on a daily basis). The number of days on average each food was consumed and the overall completion rate of adherence diaries will be used to refine plans to both monitor and boost adherence in a future longer, larger trial.

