4.1 Toxities

Side effects will be monitored by staff contact at the end of week 1 visit, and at the end of week 2 (by phone) and at the final measurement visit at the end of week 4. Participants will be encouraged to contact the Study manager during the study period if they feel they are experiencing effects related to the study foods.

EVOO and tree nuts are generally recognized as safe and are consumed by free living adults on a regular basis. The amount to be given in this study are within the range given to the participants in the PREDIMED study [6] and found to have only minor side effects, mainly stomach upset, bloating and nausea, and none of the side effects advanced to serious adverse events.

Administration

Study foods will consist of one ounce of tree nuts per day and two tablespoons of EVOO per day. Participants will be instructed how to consume the proper amount of tree nuts and EVOO and reporting the consumption on the compliance diary (Appendix A). The tree nuts will be provided in daily servings (one ounce per day) and EVOO will be provided in bottles, along with a tablespoon. Participants will be instructed to use the tablespoon to measure EVOO. Participants will also receive recipes and other written information that will assist them in incorporating both the nuts and EVOO into their existing dietary patterns.

Dose Modification/Toxicity management:

Side effects will be monitored via the telephone visit at the end of week 1 and 2 and by participant report. Participants will be encouraged to contact the study team during the study period if they feel they are experiencing side effects related to the study foods. For those participants with existing medical conditions (e.g., gallbladder removal or bariatric surgery) or who are experiencing nausea related to consumption of the olive oil, a titrated dosing plan will be used. These participants will begin their olive oil consumption at 1 tablespoon/day for 5 days and increasing to 2 tablespoons/day on the sixth day if it is well tolerated. If this increase is not tolerated, the participant can be returned to 1 tablespoon per day and attempt an increase after an additional 5 days.

Withdrawal from study intervention

Any side effects experienced by the participant may or may not be due to the study foods. If the side effects become intolerant for the participant, he/she may be withdrawn from the study at the discretion of the study team.

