5. THANK YOU FOR BEING A PART OF THIS STUDY!

	Day 1	Day 2	Day 3	Day 4	Day 5	Day 6	Day 7
Day of Week	MON	TUE	WED	THU	FRI	SAT	SUN
Date (MM/DD)	/	/	/	/	/	/	/
.							
Did you consume a one ounce portion of nuts today?	Yes No						
Did you consume 2 tablespoons of olive oil today?	Yes No						

Adherence Diary

Comments:

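### The low-adherence label tolerates no missed day, and the diary's oil item can score permitted titration days as No, which lowers Primary Outcomes 2 and 4

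*Combined protocol and SAP*

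**What the plan says.** Section 8.2 makes three diary-based proportions primary outcomes: EVOO (Outcome 2), nuts (Outcome 3) and the two together, "Primary Outcome 4: proportion of days for which EVOO and tree nuts were taken". At participant level, "Adherence for each participant will be measured as the proportion of days in 4 weeks for which nuts, and of EVOO were taken". None of these has a cut-off.

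The same section then adds two categories: "Problems associated with consuming the study foods will be defined as non-adherence (ceasing to consume either or both study foods) and low adherence". The second is spelled out as "low adherence (not consuming both foods", and it ends, running into the next sentence, with "on a daily basis). The number of days on average each food was consumed". No number of permitted misses is given. That next sentence names what will inform adherence plans for a later trial: the average days each food was consumed and the diary completion rate.

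Three other places determine what a Yes for oil means:

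- **Appendix A (the diary form)** asks: "Did you consume 2 tablespoons of olive oil today".
- **Section 5.3** describes the same diary item as asking only whether the oil was consumed that day, with no amount.
- **Section 4.1**, for participants with certain existing conditions or with nausea from the oil, says: "These participants will begin their olive oil consumption at 1 tablespoon/day for 5 days". It moves to 2 tablespoons on the sixth day if tolerated. If not, it allows a return to 1 tablespoon and another attempt after 5 more days.

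**The concern.** There are two separate problems.

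The first is the label. Read literally, a single day without one of the foods puts a participant in the low-adherence class, which Section 8.2 calls a problem. The class then holds people who missed 1 day together with people who missed 20. A feasibility report built on it could suggest widespread difficulty when intake was good.

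The second is the scoring of oil, and it reaches the primary outcomes. On the Appendix A form, a participant on the Section 4.1 titration who answers accurately must record No on a day when oil was taken as instructed. Under the Section 5.3 wording the same day could be a Yes. Section 8.2 counts days on which EVOO was taken but does not say what amount qualifies. Two analysts could therefore give the same participant different values of Primary Outcomes 2 and 4. The average days of oil use, which Section 8.2 does name as a planning input, would move with them.

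**Working it through.** **Inputs from the documents.** 4 weeks = 28 diary days (Section 8.2); the label rule (Section 8.2); two forms of the oil item (Appendix A and Section 5.3); 5 days at 1 tablespoon, with a possible further 5 (Section 4.1).

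**Assumed inputs.** The daily probability p of taking both foods, and the within-person correlation of misses. The documents give neither, so ranges are shown.

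**The plan's own figure.** There is none for adherence. The only power figure (Section 8.6: 0.80 for 0.4 SD with 50 participants) concerns epigenetic age. It reproduces (0.792 by a two-sided one-sample t-test, 0.807 by the normal approximation) and has no bearing here.

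**Step 1. One missed day.** 27/28 = 96.4%, which is low adherence on the literal wording.

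**Step 2. Share labelled, independent days.** Share = 1 − p^28.

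| p | Labelled low |
|---|---|
| 0.90 | 94.8% |
| 0.95 | 76.2% |
| 0.97 | 57.4% |
| 0.98 | 43.2% |
| 0.99 | 24.5% |

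The share passes one half only when p is below 0.5^(1/28) = 0.9755.

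**Step 3. Share labelled, misses clustered within people.** Beta-binomial with mean m and correlation ρ, a = m(1/ρ − 1), b = (1 − m)(1/ρ − 1); share = 1 − P(28 of 28). The last column restricts to people with at least 23 of 28 days (80% or more).

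| m | ρ | Labelled low, all | Labelled low, among 80% or more |
|---|---|---|---|
| 0.90 | 0.1 | 74% | 69% |
| 0.90 | 0.3 | 48% | 37% |
| 0.90 | 0.5 | 33% | 20% |
| 0.95 | 0.1 | 49% | 45% |
| 0.95 | 0.3 | 28% | 21% |
| 0.95 | 0.5 | 18% | 11% |
| 0.98 | 0.1 | 23% | 22% |
| 0.98 | 0.3 | 12% | 9% |

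**Step 4. Titration days and the primary outcomes.** Take a participant who follows Section 4.1 exactly and misses nothing. Maximum score on Outcomes 2 and 4:

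| Days at 1 tablespoon | Appendix A item | Section 5.3 item, if any oil counts |
|---|---|---|
| 5 | (28 − 5)/28 = 23/28 = 82.1% | 28/28 = 100% |
| 10 | (28 − 10)/28 = 18/28 = 64.3% | 28/28 = 100% |

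Outcome 3 (nuts) is unaffected. If all 50 are randomised 1:1, giving 25 per arm, each such participant lowers an arm mean by up to (5/28)/25 = 0.7 percentage points for 5 days, or (10/28)/25 = 1.4 points for 10. The number who will titrate is not given.

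**Step 5. Would a numerical cut be enough?** With independent days, a cut at under 80% (22 or fewer of 28) would label 0.2% at p = 0.95, 5.5% at 0.90 and 23.5% at 0.85. It would still label a fully compliant participant with 10 titration days (64.3%) under the Appendix A item. A cut alone does not settle the scoring.

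**The case against.** The label does little work. Primary Outcomes 2 to 4 are continuous and already separate 1 missed day from 20. The label enters no stated test, success criterion or participant-management rule. The later trial is to be planned from average days and diary completion, not from the label. All of this stands, and it confines the label's effect to the descriptive report.

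A reader might infer that most highly adherent participants would be classed as low adherers, and that the larger trial would be misplanned as a result. The documents do not support this. They give no expected adherence rate and no definition of high adherence. Under independence, a majority is labelled only below about 97.6% daily adherence, and Step 3 shows that moderate clustering can bring the share well under one half.

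It can also be said that daily consumption may mean a habitual pattern, not every single day. That reading is possible, but it leaves the category with no numerical boundary, so the text needs rewording either way.

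On titration, the objection is that it applies only to some participants, that the Section 5.3 item could score those days as Yes, and that someone titrating because of nausea does have a problem with the food. The first is true and limits the size. The second is the inconsistency itself, since the form participants complete is the one in Appendix A. The third may justify reporting a tolerability problem. It does not justify counting a day on which oil was taken as a day on which it was not.

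**Conclusion.** The point holds in two parts of unequal weight.

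The scoring conflict between Sections 4.1, 5.3 and 8.2 and Appendix A is the more important, and needs no assumption about adherence rates. For an affected participant, Primary Outcomes 2 and 4 are capped at 82% after 5 titration days and 64% after 10 under one diary wording, and at 100% under the other. The effect on arm means depends on how many titrate, which is unknown.

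The zero-tolerance label is a lesser defect. That 27 of 28 days falls in the low class follows from the literal wording. How many people would be so labelled rests wholly on assumed rates and on independence. The damage is limited to a descriptive category that merges occasional with frequent misses. Both parts should be corrected; neither undermines the choice of continuous primary outcomes.

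**What to change.** 1. Reconcile Sections 4.1, 5.3 and 8.2 and Appendix A for scoring purposes, without changing any dose. Use one diary wording throughout, and let it record reduced oil intake separately from none.
2. State in Section 8.2, before the diaries are analysed, one rule for scoring protocol-permitted titration days in Primary Outcomes 2 and 4. Repeat both outcomes under the other scoring as a sensitivity analysis. Identify titration days for each participant so that the rule can be applied.
3. Replace the every-day label with a graded table of the share of the 28 days on which both foods were taken, for example at least 90%, 80–89%, 50–79% and under 50%. Keep the continuous proportions as the primary outcomes. Any single cut, such as 80%, is a convention, and no conclusion should rest on it.

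Cost: slightly more detail in the diary, one extra descriptive table and revised wording in the listed sections. Diaries already completed on the Appendix A form cannot by their Yes/No answer separate 1 tablespoon from none, so for those the sensitivity analysis carries more of the weight.

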8.3 Participants' perception of epigenetic age, challenges and motivators

Primary outcome 5: Perception of Epigenetic Aging Assessment and Intervention Experience Assessment

To gain preliminary data supporting the feasibility of testing epigenetic age acceleration as a motivating factor for behavior change in a larger trial, participants of the intervention arm 1 (participants educated about epigenetic age acceleration), will be given a self-administered exit questionnaire to qualitatively explore participants' perception of epigenetic age. All participants will be given a self-administered Intervention Experience Assessment to explore participant experiences in the study, and the challenges and motivators for behavior change during the intervention. The \ questions will be designed to ascertain understanding of epigenetic age, and assess the challenges and motivators participants encountered during the intervention. All participants will be asked if they can be contacted for future studies.

8.4 Test for changes in epigenetic age acceleration

Secondary outcome: Changes in epigenetic age acceleration

It is not clear if changes in nut and EVOO consumption can slow or reverse epigenetic age acceleration. As a secondary goal, we will compare change in epigenetic age acceleration from the baseline visit to the intervention visit (control period) to change in epigenetic age acceleration from the intervention visit to the final visit using a paired sample t-test.

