4.0 Treatment Plan: Tree Nuts and Extra Virgin Olive Oil

At the intervention visit, all participants will receive the full 4-week supply of EVOO and tree nuts, including unsalted English walnuts, almonds or pistachios (approximately 10-day supply of each type). Participants will be asked to supplement their normal diets with these products and will be provided recipes and other information that will allow them to replace other foods with the nuts and oil. We will ask participants to consume one ounce of tree nuts per day and two tablespoons of EVOO per day by incorporating these foods into their diet. Dietary adherence diaries will be given to measure incorporation of the study foods.

Participants will be randomized to learn about epigenetic age acceleration (arm 1) or not to learn about epigenetic age acceleration (arm 2) in a 1:1 allocation at the intervention visit. Those in the intervention arm 1 that are to learn about epigenetic age acceleration will receive some educational materials and a brief description of epigenetic age acceleration.

A telephone visit will be conducted at the end of week 1 for additional diet counseling, to assess safety/potential side effects, to collect adherence diaries. A follow-up phone call for compliance assessment and to answer participant questions will be conducted at the end of week 2. A final measurement visit will be scheduled for the end of week 4 for a morning time and participants will be asked to be fasting.

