4.3.2 Intervention visit

Eligible participants (those that provided informed consent, were fasting at the in-person visit and met the criteria for MetS, and provided blood samples for epigenetic age acceleration

measurements) will be contacted to schedule the intervention visit. The study is set to end on March 21, 2022, which means the study intervention visits need to be completed by March 3, 2022. Participants that have not attended their intervention visit by March 3, 2022 will be discontinued from the study.

At the intervention visit, participants will have a fasting blood collection. Participants will receive counseling and recipes to help them incorporate the nuts and EVOO into daily meals. Dietary adherence diaries will be given to participants to measure incorporation of the study foods and participants will be instructed to complete the adherence diaries on a daily basis. Participants will be given a 4-week supply of EVOO, tree nuts, and a tablespoon for measuring the EVOO.

Participants will be randomized to learn about epigenetic age acceleration (arm 1) or to not learn about epigenetic age acceleration (arm 2) in a 1:1 allocation at the baseline visit. Those in arm 1 will receive some educational materials and a brief explanation of epigenetic age acceleration. At the end of this visit, all participants will be scheduled for the remainder of their telephone and in person study visits.

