8.0 Statistical Considerations

Objectives: This feasibility study, incorporating epigenetic age estimates with a nuts and EVOO intervention in individuals with MetS, is an initial step in building our understanding of the relationship between metabolic syndrome and epigenetic age and how epigenetic age estimates may be perceived by participants with MetS. This study will provide preliminary longitudinal data examining the potential to slow epigenetic age acceleration after a 4-week nuts and EVOO intervention. This longitudinal study is designed to provide pilot information that will be used to design a larger study of the effects of the nuts and EVOO on epigenetic aging. This line of work will be an important foundation towards translating epigenetic age prediction from a research concept towards a tool to meaningfully promote healthy lifestyle changes to improve cardiometabolic health among individuals at high risk for cardiovascular disease.

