8.5 Test for changes in MetS-related traits

Exploratory outcomes: Changes in body mass index, waist circumference, blood pressure, HDL cholesterol, triglycerides, HbA1c, and fasting glucose levels

Although longer clinical trials involving daily consumption of EVOO and nuts have observed improvement in MetS-related traits, it is unclear if improvements in MetS-related traits will be observed after 4-weeks. As an exploratory analysis, we will test for changes in MetS-related traits before vs. after the 4-week intervention, including changes in body mass index, waist circumference, HDL cholesterol, triglycerides, HbA1c, and fasting glucose levels using a paired sample t-test.

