8.6 Sample size justification

The prevalence of epigenetic age acceleration in people with metabolic syndrome is unknown. Also, it is unknown if a short term nuts and EVOO intervention will have measureable effects on estimates of epigenetic age. Thus, this pilot study will provide feasibility data necessary to estimate sample sizes for larger trials. Assuming 50 individuals and a type 1 error rate of $\alpha=0.05$, the study has 0.80 power to detect difference of 0.4 standard deviations in the difference in epigenetic age and chronological age. We acknowledge that power is a limitation of the current study, and designed the study to maximize the sample size based on budget constraints to provide prevalence and potential effect size estimates to guide power calculations when planning a future larger, longer trial.

References

3. Grundy SM: **Pre-diabetes, metabolic syndrome, and cardiovascular risk.** *J Am Coll Cardiol* 2012, **59**:635-643.
5. Grundy SM: **Metabolic syndrome update.** *Trends Cardiovasc Med* 2016, **26**:364-373.

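### Sections 8.4 and 8.5 pool the educated and non-educated arms, so the pooled change is a programme effect and should be labelled so, with change by arm beside it

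*Combined protocol and SAP*

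**What the plan says.** All participants are given the study foods. Section 4.0 assigns them to learn about epigenetic age acceleration (arm 1) or not ("arm 2) in a 1:1 allocation at the intervention visit"). Section 4.3.2, on the visit at which the foods are handed out, adds: "Those in arm 1 will receive some educational materials and a brief explanation of epigenetic age acceleration".

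For the secondary outcome, Section 8.4 compares change over a control period (baseline visit to intervention visit) with "change in epigenetic age acceleration from the intervention visit to the final visit using a paired sample t-test". For the exploratory outcomes, Section 8.5 states that "we will test for changes in MetS-related traits before vs. after the 4-week intervention", again by paired t-test and without a control period. Neither section mentions arm, and nor do Objectives 1.2 and 1.3. The only between-arm comparison named in the objectives is adherence (Section 1.1).

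Section 8.4 frames its question as whether eating nuts and olive oil affects epigenetic age acceleration. Section 8.0 says the pilot will inform the design of a larger study of those foods. The same section hopes that epigenetic age prediction will become "a tool to meaningfully promote healthy lifestyle changes to improve cardiometabolic health".

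**The concern.** Two things begin at the intervention visit: the foods, for everyone, and the education, for half. A paired test over everyone cannot separate them. If the education also prompts arm 1 to exercise more or to change the rest of their diet, part of the pooled change belongs to the education, yet the plan's framing credits it to the foods. At stake are what the pilot can say about the foods and the effect size it hands to the larger study. The factor that would show the difference is randomised and recorded, but the biological analyses do not use it.

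The concern is limited to effects through other habits. If education makes people eat the nuts and oil more faithfully, the resulting change is still an effect of the foods.

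**Working it through.** **1. Is the analysis pooled?** The text is silent on arm, so the sample size statement is the check. Section 8.6 takes 50 individuals and a type 1 error rate of 0.05 and says "the study has 0.80 power to detect difference of 0.4 standard deviations". Two-sided testing is assumed, since sidedness is not given.

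- One group of 50, paired t-test: noncentrality 0.4 × √50 = 2.83, df 49, power 0.79 (normal approximation 0.81). This reproduces 0.80.
- Two groups of 25: noncentrality 0.4 × √(25/2) = 1.41, df 48, power 0.28. This does not.

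The plan's figure is a single-group calculation on everyone. It concerns the gap between epigenetic and chronological age rather than the Section 8.4 contrast, so it supports pooling without settling it.

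**2. Where an education effect goes.** Let D be each participant's contrast: in Section 8.4, (final − intervention) − (intervention − baseline); in Section 8.5, after − before. Let f be the mean of D without education, and e the extra mean change in arm 1 through habits other than the study foods. With 25 per arm (1:1 of 50, no dropout assumed):

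pooled mean = [25f + 25(f + e)] / 50 = f + e/2.

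The Section 8.4 control period ends at the visit where the education is described, so subtracting it leaves e untouched. Section 8.5 has nothing to subtract.

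The timing is not fully consistent. Section 4.0 puts randomisation at the intervention visit; Section 4.3.2 puts it at the baseline visit, and Section 1.1 speaks of education at baseline. If education were given at baseline, part of its effect would fall inside the control period. These passages need to be reconciled.

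**3. Illustration.** Assumptions not in the documents: SD of D = 1 in each arm, normal errors, f = 0, and the values of e. From 100,000 simulated trials at a nominal two-sided 5%:

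| e (SD) | shift in pooled mean, e/2 | pooled test rejects | arm 2 alone rejects |
|---|---|---|---|
| 0 | 0 | 5.0% | 5.0% |
| 0.1 | 0.05 | 6.3% | 5.0% |
| 0.2 | 0.10 | 10.5% | 5.0% |
| 0.3 | 0.15 | 17.6% | 5.0% |
| 0.4 | 0.20 | 27.2% | 5.0% |

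The arm 2 column stays at 5% because the simulation sets time trends and every other influence on arm 2 to zero.

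**4. What relying on arm 2 costs.**

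- Standard error: pooled 1/√50 = 0.141; arm 2 1/√25 = 0.200; ratio √2 ≈ 1.4.
- Power at 0.4 SD: pooled 0.79; arm 2 alone 0.48 (0.50 if the residual SD is taken from both arms). Difference detectable with 0.80 power: 0.40 SD pooled, 0.58 SD in arm 2.
- Arm 1 minus arm 2: power 0.28 at 0.4 SD; 0.81 SD is needed for 0.80 power.
- Mean squared error as an estimate of f: pooled 1/50 + e²/4; arm 2 1/25. They are equal when e² = 4 × (0.04 − 0.02) = 0.08, that is e ≈ 0.28. At e = 0.2 the pooled estimate is better (0.030 against 0.040); at e = 0.4 it is worse (0.060 against 0.040).

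**The case against.** The strongest reply is that e is probably small. The education is a short generic explanation with written materials, and follow-up lasts four weeks. No step tells participants their own value: Section 5.2 sends samples for methylation analysis only after recruitment of 50 is complete, and Appendix D asks about being told one's epigenetic age as a hypothetical. This stands, and it limits how much weight the table can bear.

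A reader might infer that the protocol itself predicts an effect of education on other habits. It does not. The hypothesis in Section 1.0 is that learning about epigenetic age improves adherence to the dietary intervention. The associations with physical activity and diet cited there describe epigenetic age acceleration, not education. The lifestyle passage in Section 8.0 describes where the line of work may lead, and Section 8.3 looks to a larger trial for testing epigenetic age as a motivator. These make the pathway plausible, no more.

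A reader might also infer that arm 2 gives a clean foods-only answer that should replace the pooled one. It does not. Arm 2 also receives counselling, recipes, diaries and telephone calls (Sections 4.0, 4.3.2 and 4.3.3). In Section 8.5 its change is an uncontrolled before-after change in people selected on thresholds for several of the same traits (Section 2.1), so regression to the mean remains. For e below about 0.28 SD the pooled estimate is also the more accurate of the two.

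Finally, these are secondary and exploratory outcomes of a pilot that acknowledges limited power, and Objectives 1.2 and 1.3 promise only a comparison across the four-week intervention. The pooled test answers that. What it does not support unaided is attribution to the foods.

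**Conclusion.** The point holds as one of labelling and reporting. The pooled change in Sections 8.4 and 8.5 estimates the programme as delivered, and any education effect through other habits enters it at half size, without being removed by the control period (Section 8.4) or by any comparison (Section 8.5). This rests on reading silence about arm as pooling, on education being given at the intervention visit, and on roughly equal arms.

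The size is unknown. The 10% to 27% range depends on assumed shifts of 0.2 to 0.4 SD with no foods effect; it is not an estimate of this study's error rate. The 0.4 SD in Section 8.6 lends it no support, because that figure concerns another quantity. The documents do not support calling the pooled test invalid or making arm 2 the default estimate for sizing the larger study.

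**What to change.** Keep the pooled paired test as the planned analysis in Sections 8.4 and 8.5, and label its result the effect of the programme as delivered: foods and counselling, with education in half the participants.

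Beside it, fit D = b0 + b1 × (arm 1) + error for each outcome, coding arm 2 as zero. Report, as descriptive estimates with 95% confidence intervals, mean change in arm 2 (b0), mean change in arm 1 (b0 + b1) and the arm 1 minus arm 2 difference (b1). A centred arm term would not serve, because it still estimates the average over arms, f + e/2.

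Use the arm 2 change as a sensitivity check before attributing the pooled change to the foods or carrying it into the larger study's sample size. State that arm 2 also had counselling, recipes, diaries and calls, and that Section 8.5 has no control period. Reconcile Sections 1.1, 4.0 and 4.3.2 on when randomisation and education take place.

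The cost is a few sentences and one regression per outcome, with no new data. The by-arm results will be imprecise: about 25 people per arm at most, an arm 2 interval about 1.4 times as wide as the pooled one, and power of about 0.28 for an arm difference of 0.4 SD. A null arm difference should therefore not be read as showing that education had no effect.
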